# 13.5 Contraception and pregnancy

Exercise and physical activity is not contra-indicated in pregnancy, Current clinical evidence points towards the maintenance of an exercise of a program during pregnancy as beneficial to both mother and child, therefore, this pragmatic trial will not advise that pregnancy be prevented during this trial.

# 13.5.1 Contraception

Women of Child Bearing Potential (WOCBP) entering into this trial will not be asked to take contraception during the trial as a condition of participation.

# 13.5.2 Pregnancy reporting whilst participating in the trial

Pregnancy occurring whilst participating in the trial, is not considered an SAE, however, an issue with the pregnancy, a congenital anomaly or birth defect is. Other cases (e.g. termination of pregnancy without information on congenital malformation, and reports of pregnancy exposure without outcome data) should not normally be reported as such. When pregnancy occurs, this should be followed up until the end of the participant's involvement in the trial or until the end of pregnancy, whether that is a live birth, abortion etc. Without follow-up of the pregnancy, it would not be possible for the CTR to know if a pregnancy issue, congenital anomaly or birth defect occurred, and therefore if there was an SAE that must be included in the safety evaluation of the intervention. Information on a pregnancy in a trial participant will be captured on the CTR Pregnancy Report Form supplied to sites by the CTR.

Sites should report any pregnancy occurring during the course of the intervention. For any pregnancies occurring in participants of the longitudinal observational study these do not need to be reported. Issues occurring during the pregnancy, congenital anomalies or birth defects are considered an SAE and so these events must also be reported to the CTR on a trial-specific SAE form and should be submitted to the CTR within the timeframes stipulated for SAE reporting.

# 13.6 Urgent Safety Measures (USMs)

An urgent safety measure is an action that the Sponsor or Chief Investigator may carry out in order to protect the subjects of a trial against any immediate hazard to their health or safety. It is extremely unlikely that any urgent safety measures should be required for this trial, but any urgent safety measure relating to this trial that does occur must be notified to the local Institutional Review Board (IRB) immediately by telephone, and in any event within 3 days in writing, that such a measure has been taken. USMs reported to the CTR will be handled according to CTR processes.

#### 14 Statistical considerations

#### 14.1 Randomisation

A minimisation technique will be used for randomisation to allow for balancing of age (above or below age 50 years) and motor impairment (above or below UHDRS total motor score 40) at baseline. The randomisation will be stratified by country. A Randomisation schedule will outline all randomisation procedures, implementation and back-up system.

#### 14.2 Blinding

There will be no blinding of participants or assessors in the nested RCT. The nature of the intervention means that participants cannot be blinded however there are a range of quantitative outcomes that will be collected in an attempt to minimise bias.

# 14.3 Sample size

The primary outcome for this trial is feasibility of a within cohort nested RCT of a 12-month exercise intervention in terms of; data completeness, recruitment, retention, fidelity and acceptability. For a total sample size of 120 participants recruited into the cohort study we are able to determine a 95% confidence interval for 70% retention rate to within +/- 8.2%.

In line with the primary feasibility objectives of the trial a formal calculation has not been carried out to determine the sample size for the RCT. Formal hypotheses testing will not be carried out and only effect sizes and 95% confidence intervals will be provided for the interpretation of outcomes

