# 5.3 Primary outcomes measure(s)

The primary outcome measures for this trial are focused on feasibility of the 12-month physical activity intervention.

- Recruitment rate will be assessed using site recruitment logs.
- Retention rate will be measured as the percentage of individuals who completed the intervention.
- Adherence rates will be defined as percentage of intervention sessions completed,
- Safety will be assessed through monthly documentation completed by therapists administering the intervention, which captures information on falls history, medication

changes, healthcare service use and hospital admissions (classified as serious adverse events).

- Fidelity of the interventions will be assessed via review of coach documentation and activity monitor data.
- Data completeness will be assessed by the percentage of data entered into the database.

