# 6 Trial design and setting

This trial is a longitudinal observational study of physical activity and physical fitness in 120 people with early-mid stage HD (assessed as having an overall low risk) with an additional nested evaluation of a 12-month physical activity intervention (n=30) compared to usual activity (n=30).

Participants will be recruited from current Enroll-HD sites in Europe and the USA. Enroll-HD is a worldwide research platform that has as its core a longitudinal observational study of HD families. Enroll-HD provides an infrastructure to support clinical studies such as the one proposed here. Recruitment for the longitudinal study and the nested RCT will be conducted over a period of 15 months, both with a 12 month follow up period. The trial is expected to last a total of 27 months. The end of the trial will be defined as last participant, last visit, which will be the 12-month assessment. This could be a participant in either the observational cohort or nested RCT.

All participants will undergo a baseline assessment as part of their annual Enroll-HD visit where standard measures will be collected as per the Enroll-HD study protocol. Additional assessments pertaining to physical activity will also be performed (see section 12.1 for further details). The additional assessments should be collected  $\pm$  4 weeks of the annual ENROLL visit. These assessments will be repeated after 12 months within  $\pm$  4 weeks of the next annual Enroll-HD visit. For those participants taking part in the nested RCT, an additional assessment will be performed at 6 months. For participants randomised to receive the physical activity and coaching intervention in the nested RCT, they will receive the intervention over a 12-month period which will include 18 home or site visits (pragmatically scheduled) and additional supportive monthly telephone calls.

All data will be entered directly into the trial database by local researchers via an individual log-in. Where data is obtained from third party sources exports will be obtained on a monthly basis for upload into the trial database.

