#### 10.2 Loss to follow up

For the longitudinal observation study we do not anticipate a high rate of loss to follow up due the participant's ongoing involvement in Enroll-HD. We will adhere to the Enroll-HD protocol for managing lost to follow up participants in the observational cohort.

For participants in the nested RCT, participants will be deemed to be lost to follow up if they fail to attend more than 4 consecutive coaching contact sessions.

As this is a pragmatic trial, if a participant meets the criterion of lost to follow up, no further direct efforts will be made to engage with that participant. As all participants will be participants of Enroll-HD, we will be able to obtain a proportion of 12-month assessment data for all participants unless they are lost to follow up in the Enroll-HD study. Remote data from FitBit activity monitors will also be collected from those lost to follow up.

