#### a. Feasibility

Summary data for recruitment, retention and data completeness will be tabulated for the cohort and nested RCT. Adherence rates, safety and fidelity will also be summarised for the RCT.

b. RCT

The individually randomised data from the three sites will be explored.

The analysis will compare

- I. Linked Enroll-HD data for participants between the two groups at 1 year
- II. PACE-HD trial data (see section 12.1)

Linear models will be used for key continuous outcomes, controlling for individual participant characteristics used to balance the randomisation as baseline covariates. Treatment effects will be summarised using regression coefficients, 95% confidence intervals and standardised effect sizes. Standard diagnostics will be performed to ensure adequate model fit (including inspecting fitted versus residual plots). The analysis will be intention to treat and complete case.

Analysis of secondary outcomes will proceed similarly, with linear regression used for continuous outcomes and logistic regression for dichotomous outcomes. A mediation analysis will be performed on the physical fitness measure recorded at 6 months. No inflation for clustering has been included in the power calculation however a sensitivity analysis will be conducted using hierarchical modelling to explore the extent of clustering in the primary outcome variable by site.

Progression criteria to proceed to further evaluation will be based on the following; over 60% drop out from the RCT at 12 months will mean no progression, between 40 and 60 % drop out will mean that changes to the intervention and/or follow-up procedures will be required and less than 30% drop at 12 months will indicate that the intervention is suitable for further evaluation without modification.

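### The only precision figure for retention (±8.2 points) holds for the whole cohort of 120, not for the RCT (n=60) or the intervention arm (n=30) on which feasibility is judged

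*Protocol*

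**What the plan says.** Protocol section 14.3 opens with "The primary outcome for this trial is feasibility of a within cohort nested RCT of a 12-month exercise intervention" and lists retention among its components. The next sentence gives the only precision statement in the protocol: "For a total sample size of 120 participants recruited into the cohort study we are able to determine a 95% confidence interval for 70" per cent retention, to within 8.2 percentage points. The paragraph after that says no formal calculation was done for the size of the RCT, and that outcomes will be interpreted through effect sizes and 95% confidence intervals.

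Three other places bear on what retention means:

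- Section 5.3, on the primary outcomes: "Retention rate will be measured as the percentage of individuals who completed the intervention".
- Section 15.1, on progression: "over 60% drop out from the RCT at 12 months will mean no progression". Drop-out of 40 to 60% means changes are required, and under 30% means the intervention can go forward unmodified. The same section tabulates retention for both the cohort and the nested RCT.
- Section 10.2: "For the longitudinal observation study we do not anticipate a high rate of loss to follow up", because these participants remain in Enroll-HD.

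The planned numbers are 120 in the cohort, 60 in the RCT (section 4.1), 30 per arm (section 6) and 60 in the observational part only (section 12).

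**The concern.** The precision statement and the quantity being judged rest on different groups of people. The sample size section announces an RCT feasibility outcome and then quotes precision for a group of which half never enters the RCT. Neither the retention outcome in section 5.3 nor the drop-out rule in section 15.1 has 120 as its denominator.

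The 70% used for the calculation is the complement of the 30% drop-out threshold for unmodified progression. A reader will therefore naturally attach ±8.2 points to that threshold, where it does not apply, and will think the RCT result separates the progression bands better than it can.

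The groups may also differ in retention, not only in size. Section 10.2 anticipates no high loss among observational participants and makes no similar statement for the RCT. A retention figure pooled over all 120 may therefore be higher than the RCT's own.

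**Working it through.** **Inputs.** Retention p = 0.70, 95% two-sided interval and stated half-width 8.2 points (section 14.3). Denominators: 120, 60 and 30 (sections 14.3, 4.1 and 6).

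**Step 1: reproduce the plan's figure.** Normal-approximation half-width = 1.96 × √(p(1−p)/n).

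n = 120: 1.96 × √(0.21/120) = 1.96 × 0.04183 = 0.0820, or 8.2 points. This matches.

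Solving back, n = 0.21 × (1.96/0.082)² = 119.97, so the figure rests on the whole cohort.

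**Step 2: same formula, the denominators that feasibility uses.**

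n = 60: 1.96 × √(0.21/60) = 1.96 × 0.05916 = 0.1160

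n = 30: 1.96 × √(0.21/30) = 1.96 × 0.08367 = 0.1640

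| Group | n | Half-width at 70% | Ratio to n = 120 | Exact (Clopper-Pearson) 95% interval |
|---|---|---|---|---|
| Whole cohort | 120 | 8.2 points | 1 | 84/120: 61.0% to 78.0% |
| RCT | 60 | 11.6 points | √2 = 1.41 | 42/60: 56.8% to 81.2% |
| Intervention arm | 30 | 16.4 points | √4 = 2.0 | 21/30: 50.6% to 85.3% |

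**Step 3: set against the progression thresholds.** Take an observed RCT drop-out of 18/60 = 30%, the edge of the band for unmodified progression.

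- With the stated precision: 30 ± 8.2 = 21.8% to 38.2%, which stops short of 40%.
- With the RCT denominator, normal approximation: 30 ± 11.6 = 18.4% to 41.6%.
- With the RCT denominator, exact: 18.8% to 43.2% (the complement of the 42/60 interval).

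Both RCT intervals start in the band for unmodified progression and end in the 40 to 60% band. The stated ±8.2 would suggest that the latter is excluded.

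**The case against.** There is a fair case for the text as it stands. The 8.2 is right for 120, and section 14.3 says plainly that it refers to cohort participants. The same section discloses that the RCT size was not formally calculated, which is acceptable for a feasibility study. Section 15.1 tabulates retention for the cohort as well as the RCT, so a cohort precision has a planned use, and separate reporting of the two is already intended. The progression rule is worded on the observed drop-out percentage, so no analysis or decision uses the 8.2.

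All of this stands, and it limits the point to a mismatch of populations. It does not remove the point: neither the disclosure nor the tabulation supplies a precision for the quantity on which progression is decided, and the cohort figure sits directly under the RCT outcome as its only numerical support.

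Two stronger readings are tempting. A reader might infer that the progression decision is only half as precise as stated. The factor of two belongs to the intervention arm; the rule is set on the RCT, where the factor is 1.4. A reader might also infer that observational participants will inflate the retention figure used for progression. Section 15.1 applies the rule to RCT drop-out, nothing says that a pooled figure will feed it, and section 10.2 does not predict that cohort retention will exceed RCT retention. Only the weaker statement is supported: pooling may raise the figure.

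**Conclusion.** The point holds as a mismatch between the stated precision and the outcome it is meant to support. It is not a calculation error, and it is not a criticism of the RCT for lacking a power calculation. At 70% retention the half-width is 11.6 points for the RCT and 16.4 for the intervention arm, against the 8.2 quoted. At 30% observed RCT drop-out, the exact interval of 18.8% to 43.2% covers more than one progression outcome.

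The figures assume recruitment as planned (60 randomised, 30 per arm), the plan's own 70%, and independent participants with no allowance for clustering by site. The choice between exact and normal-approximation intervals does not alter the conclusion. The absence of a rule for drop-out between 30 and 40% is a separate matter and adds no weight here.

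**What to change.** 1. Restate the precision in section 14.3, for example: *For 70% retention the 95% CI half-width is 11.6 points in the RCT (n=60) and 16.4 points in the intervention arm (n=30); 8.2 points applies only to the whole cohort (n=120).*
2. State which denominator is the primary retention outcome, so that sections 5.3, 14.3 and 15.1 agree. Quoting several half-widths without this would leave the definition open.
3. Report RCT drop-out with its 95% confidence interval alongside the progression thresholds. The interval method can be left to the statistical analysis plan.

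The cost is a change of text. It needs no extra participants, visits or data. The quoted precision becomes less favourable.

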# 14.4 Missing, unused & spurious data

All data will be checked prior to analysis and cleaned following standard procedures outlined in the data management and statistical analysis plans.

# 14.5 Procedures for reporting deviation(s) from the original SAP

These will be submitted as substantial amendments where applicable and recorded in subsequent versions of the protocol and SAP.

#### 14.6 Termination of the trial

Circumstances surrounding the enforced withdrawal of individual participants by the site researchers can be found in section 10.1

# 14.7 Inclusion in analysis

All participants enrolled into the cohort study will be included in the analysis of the cohort study results unless they specifically request to withdraw their data from analyses. Additionally, all participants randomised in the nested RCT will be included in the analysis of the RCT results unless they specifically request to withdraw their data.

# 15 Analysis

#### 15.1 Main analysis

Descriptive statistics will summarise the key demographics and patient characteristics of the cohort. The formal analysis will be conducted in two parts.

#### a. Feasibility

Summary data for recruitment, retention and data completeness will be tabulated for the cohort and nested RCT. Adherence rates, safety and fidelity will also be summarised for the RCT.

b. RCT

The individually randomised data from the three sites will be explored.

The analysis will compare

- I. Linked Enroll-HD data for participants between the two groups at 1 year
- II. PACE-HD trial data (see section 12.1)

Linear models will be used for key continuous outcomes, controlling for individual participant characteristics used to balance the randomisation as baseline covariates. Treatment effects will be summarised using regression coefficients, 95% confidence intervals and standardised effect sizes. Standard diagnostics will be performed to ensure adequate model fit (including inspecting fitted versus residual plots). The analysis will be intention to treat and complete case.

Analysis of secondary outcomes will proceed similarly, with linear regression used for continuous outcomes and logistic regression for dichotomous outcomes. A mediation analysis will be performed on the physical fitness measure recorded at 6 months. No inflation for clustering has been included in the power calculation however a sensitivity analysis will be conducted using hierarchical modelling to explore the extent of clustering in the primary outcome variable by site.

Progression criteria to proceed to further evaluation will be based on the following; over 60% drop out from the RCT at 12 months will mean no progression, between 40 and 60 % drop out will mean that changes to the intervention and/or follow-up procedures will be required and less than 30% drop at 12 months will indicate that the intervention is suitable for further evaluation without modification.

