#### 9.5.2 Randomisation

The randomisation will be stratified by country. Participants within intervention countries will be randomised in a 1:1 ratio to receive the intervention or continue with their current regime of physical activity. A minimisation technique will be used for randomisation to ensure a similar distribution of selected participant factors between trial groups. The first participant is truly randomly allocated; for each subsequent participant, the treatment allocation that minimises the imbalance on the selected factors between groups at that time is selected. That allocation may then be used, or a choice may be made at random with a heavy weighting in favour of the intervention that would minimise imbalance (for example, with a probability of 0.8). The participant factors to be balanced in the nested RCT will be age (above or below age 50 years), gender and motor impairment (above or below UHDRS total motor score 40). The randomisation process will be automated via the PACE-HD database.

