#### 12 Trial procedures

#### Recruitment and follow-up:

Participants will be assessed at baseline, at 6 months (for participants of the nested RCT only) and at 12 months. Those enrolled in the observational cohort (n=60) and those taking part in the nested RCT and randomised to the control arm (n=30) will continue to undertake physical activity as usual. Those participants in the nested RCT randomised to receive the intervention (n=30) will receive 12 months of an individualised physical therapy intervention, coached by a physical therapist.

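### The only covariates named for the RCT models are the randomisation balancing factors; each outcome's own baseline value, which is collected, is not among them, and this gives away precision

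*Protocol*

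**What the plan says.** Protocol section 15.1, part b, fits linear models to the key continuous outcomes of the RCT, "controlling for individual participant characteristics used to balance the randomisation as baseline covariates". It then says that secondary outcomes are handled in a similar way, and that the linked Enroll-HD data are compared between the two groups at one year.

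The balancing characteristics are listed in section 9.5.2 as "age (above or below age 50 years), gender and motor impairment (above or below UHDRS total motor score 40". Section 14.1 describes the same procedure as "balancing of age (above or below age 50 years) and motor impairment (above or below UHDRS total motor score 40) at baseline", without gender. Both sections make country a stratification factor ("The randomisation will be stratified by country").

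On data collection, section 12 states: "Participants will be assessed at baseline, at 6 months (for participants of the nested RCT only) and at 12 months". Tables 1 to 3 schedule a baseline measurement for the outcomes that are measured again at 6 or 12 months. The Brunel questionnaire is scheduled there at baseline only, so the point does not apply to it.

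No section mentions the outcome's own baseline as a covariate, a change score or a repeated-measures model. Section 14.3 says that the RCT has no formal sample size calculation and no hypothesis tests, and that outcomes will be interpreted from effect sizes and 95% confidence intervals.

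**The concern.** In a randomised comparison of a continuous outcome, the baseline value of that outcome is usually the strongest single predictor of its follow-up value. Section 15.1 commits to a covariate set that does not contain it, although the value will already be in the database.

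At stake is the width of the confidence intervals, which are the RCT's whole inferential output and come from a small trial ("12-month physical activity intervention (n=30) compared to usual activity (n=30"). Minimisation balances age, gender and motor score; it does not balance baseline fitness, walking distance or cognitive scores. A chance difference between arms on one of these would stay in the treatment estimate for that outcome.

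**Working it through.** **The protocol's own precision figure.** Section 14.3 gives ±8.2% for a 70% retention rate in 120 participants. The half-width is 1.96 × √(0.7 × 0.3 / 120) = 0.0820, so it reproduces. It concerns cohort retention. The protocol gives no precision figure for the RCT treatment effect.

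**Inputs from the protocol.** 30 per arm (section 6); 1:1 allocation ("Participants within intervention countries will be randomised in a 1:1 ratio", section 9.5.2); 95% intervals (section 14.3); complete-case analysis (section 15.1). As a loss scenario, the 30% drop-out limit in the progression criteria of section 15.1 leaves 60 × 0.7 = 42 participants, 21 per arm.

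**Assumptions.**
- The correlation r between baseline and follow-up is not in the document, so a range is shown.
- Balancing factors and country take 5 degrees of freedom: three for age, gender and motor score, two for three countries. This is the same with and without the baseline value, so the comparison isolates the baseline value.
- Outside the total motor score case, the balancing factors are taken as unrelated to the outcome.

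**Formulas, in SD units of the outcome, n per arm, N in total.**
- Without the baseline value: t(0.975; N − 7) × √(2/n)
- With it: t(0.975; N − 8) × √(2/n) × √(1 − r²)

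**N = 60.** √(2/30) = 0.258 and t on 53 df is 2.006, so the half-width without the baseline value is 0.52 SD.

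| Assumed r | √(1 − r²) | Half-width with baseline (SD) | Interval narrower by |
|---|---|---|---|
| 0.3 | 0.954 | 0.49 | 5% |
| 0.5 | 0.866 | 0.45 | 13% |
| 0.7 | 0.714 | 0.37 | 29% |
| 0.8 | 0.600 | 0.31 | 40% |

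At r = 0.7 the gain is equivalent to multiplying the sample by 1/(1 − 0.49) = 1.96.

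**N = 42.** √(2/21) = 0.309 and t on 35 df is 2.030, giving 0.63 SD without the baseline value, and 0.54, 0.45 or 0.38 SD with it at r = 0.5, 0.7 or 0.8.

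**Total motor score.** If its dichotomised baseline is already in the model, part of the gain has been taken. A median split of a normal variable carries 2/π = 0.64 of r², so the starting half-width is 0.518 × √(1 − 0.64 r²).

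| Assumed r | Split only (SD) | Continuous baseline (SD) | Interval narrower by |
|---|---|---|---|
| 0.5 | 0.475 | 0.449 | 5% |
| 0.7 | 0.430 | 0.370 | 14% |
| 0.8 | 0.399 | 0.311 | 22% |

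**Check by simulation.** Models with treatment, age group, gender, motor split and country were fitted to 60 simulated participants, with and without the baseline value. Where the motor split is unrelated to the outcome's baseline, the ratio of interval widths is 0.88, 0.72 and 0.61 at r = 0.5, 0.7 and 0.8. Where the split is of the outcome's own baseline, it is 0.96, 0.87 and 0.79. Both sets agree with the formulas.

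**The case against.** The strongest reply is that section 15.1 names these covariates without calling the list complete. The protocol refers to a statistical analysis plan that is not shown, and per-outcome covariate lists often belong there. A reader might infer that the protocol rules out baseline adjustment; it does not. What remains is that the protocol does state a covariate set, and that set can be improved at almost no cost. This is a comment on a stated method, not on missing detail.

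The size of the gain is also open to challenge. It rests on correlations that the documents do not supply and is only 5% at r = 0.3. It is about half or less for total motor score if its cut form is already a covariate, and outcomes that correlate with motor score would also gain somewhat less than the first table shows. This stands, and is why a range is given.

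The motor-score cut might be read as discarding most of that variable's information. The documents do not support this. They give no distribution of the score, a median split of a normal variable keeps about 64% of the explained variance, and section 15.1 does not say that the cut forms are what enters the model.

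Finally, the effect estimates are a secondary, exploratory objective. Leaving out a prognostic covariate does not invalidate a randomised comparison. That also stands.

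**Conclusion.** The point holds as a matter of precision. The covariates named for the RCT models are the balancing factors, and the outcome's own collected baseline value is not added anywhere in the protocol. With 60 analysed, adding it would narrow the 95% interval by 5% to 40% for an assumed r of 0.3 to 0.8. For total motor score the gain is about 5% to 22% for r of 0.5 to 0.8, if its dichotomised baseline is already adjusted for. Calling the loss large would need r of about 0.6 or more (at least 20% narrower), which the document neither states nor excludes.

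Two stronger readings should not be drawn:
- **Bias or invalid intervals.** Over randomisation the estimates are unbiased and the intervals valid with or without the baseline value. Feasibility and the progression criteria, which turn on drop-out, are unaffected.
- **A faulty mediation analysis.** Section 15.1 says "A mediation analysis will be performed on the physical fitness measure recorded at 6 months" and names no covariates. One might infer that pre-existing fitness will pass as a mediated effect, but that rests on silence. The sentence fixes nothing wrongly, and the detail may lie in the analysis plan.

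**What to change.** Replace the covariate statement in section 15.1 with:

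> Linear models for each continuous outcome measured at baseline will adjust for the baseline value of that outcome (continuous), the factors used to balance the randomisation (age, gender, UHDRS total motor score, with total motor score entered once when it is the outcome) and country (the stratification factor).

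Listing the factors also settles, for the analysis, whether gender is included, since sections 9.5.2 and 14.1 differ.

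Use the accelerometer baseline as a covariate only if it is recorded before randomisation. The document disagrees on its timing: section 12 places the monitoring week after the baseline assessment, while Table 1 has the monitor given out at the consent visit and returned at baseline, and also has it given out at the end of the assessments.

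The cost is one degree of freedom for the baseline value plus those for country (two if the RCT sites are in three countries). No new data are needed. Because the analysis is complete case, a participant without the baseline value would drop out of that outcome's model, so the handling of missing baselines should be stated alongside.

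### Section 14.7 includes all randomised participants, but section 15.1 fixes a complete-case RCT analysis; reconcile the two and use the 6-month values where they exist

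*Protocol*

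**What the plan says.** - **Who is included.** Section 14.7: "all participants randomised in the nested RCT will be included in the analysis of the RCT results unless they specifically request to withdraw their data". A request to withdraw data is the only exception given.
- **How missing outcomes are handled.** Section 15.1, part b: "The analysis will be intention to treat and complete case". The models are linear or logistic regressions adjusted for the factors used to balance the randomisation.
- **Loss to follow-up.** Under section 10.2 an RCT participant is lost after missing more than four coaching contacts in a row, and the trial then makes no further direct attempt to engage them. The section expects Enroll-HD still to supply part of the 12-month data. Section 11.3 gives the control arm no intervention and no therapist visits.
- **When outcomes are measured.** Tables 1 to 3 give baseline, 6-month and 12-month values in the RCT for predicted VO2max, accelerometry, IPAQ and Lorig self-efficacy. Table 1 adds the 6-minute walk, although the RCT-only block of Table 3 does not list it. The linked Enroll-HD outcomes, Q-Motor, Q-Cog and HD-PRO-TRIAD have one follow-up, at 12 months. C3T has one, at 6 months.
- **Size and precision.** The RCT plans 30 per arm. Section 14.3 says "a formal calculation has not been carried out to determine the sample size for the RCT" and offers one precision figure, for cohort retention.

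**The concern.** A complete-case regression excludes every participant without the outcome, including people who never asked for their data to be withdrawn. An analyst who takes section 14.7 to cover the effect models cannot follow both sections.

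The choice matters because the loss-to-follow-up rule can operate only where there is coaching. Intervention participants who disengage may lose their 12-month PACE-HD assessments under a rule that cannot touch a control. Section 10.1 also names worsening health and increased falls as reasons for leaving the intervention, so those missing may differ in outcome from those who stay. Complete case is then unbiased only if missingness is unrelated to outcome given arm and the few baseline covariates. For the five measures also taken at 6 months, the trial holds later information on many of these people that the 12-month model does not use.

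**Working it through.** **1. The plan's own figure.** Section 14.3 gives a "95% confidence interval for 70% retention rate" of plus or minus 8.2 points at N = 120. Check: 1.96 × √(0.7 × 0.3 / 120) = 0.0820. It reproduces. It concerns the cohort, and section 5.3 defines retention as completing the intervention, so it does not forecast missing RCT outcomes.

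**2. How many would be excluded.** Section 15.1 sets progression bands by RCT drop-out: below 30% is acceptable without modification, 40-60% calls for changes, and "over 60% drop out from the RCT at 12 months will mean no progression". If drop-out meant a missing 12-month value (an assumption):

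| Missing at 12 months | Analysed of 60 | Excluded |
|---|---|---|
| 30% | 42 | 18 |
| 40% | 36 | 24 |
| 60% | 24 | 36 |

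**3. Precision.** Unadjusted, with equal loss in both arms, the 95% half-width of the standardised difference is 1.96 × √(2/n), with n observed per arm.

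- All 60: 1.96 × √(2/30) = 0.51 SD.
- 30% missing: 1.96 × √(2/21) = 0.60 SD.
- 40% missing (n = 18): 0.65 SD. 60% missing (n = 12): 0.80 SD.

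If everyone who leaves has a 6-month value, and ρ is the correlation between 6 and 12 months, the variance per arm becomes (1/n) × [1 − ρ²(1 − n/30)]. The protocol gives no ρ; 0.5 to 0.8 is assumed. At 30% missing:

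- ρ = 0.5: (1 − 0.25 × 0.3)/21 = 0.0440, half-width 0.58 SD.
- ρ = 0.8: (1 − 0.64 × 0.3)/21 = 0.0385, half-width 0.54 SD.

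The interval narrows by about 4% to 10%. Outcomes with a single follow-up gain nothing.

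**4. Bias.** If non-completers are worse than completers by δ, and a fraction m is missing, the completers' mean exceeds the arm's true mean by m × δ. The contrast is therefore biased by δ × (m in intervention − m in control). Assume δ = 0.3 to 0.5 SD and 30-40% missing against 10%:

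- Smallest: 0.3 × (0.30 − 0.10) = 0.06 SD.
- Largest: 0.5 × (0.40 − 0.10) = 0.15 SD.

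This scenario loses 12 to 15 of 60 (9 + 3 or 12 + 3), so it differs from the 18 of 60 in step 2.

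**5. Do the 6-month values help with bias?** In a simulation with no true effect, 30% loss in the intervention arm only, ρ = 0.7, and drop-out depending on the 6-month value (logistic slope 1 per SD), complete case was biased by about 0.18 SD. Using the 6-month value brought this to 0.00. The missingness is at random by construction, so this shows what can be gained when that assumption holds.

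**The case against.** A reader might infer four stronger things, and the protocol does not support them.

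- **That intention to treat and complete case contradict each other.** They can coexist: the first can mean analysed as allocated, which section 9.4 supports, and the second says how missing outcomes are treated. Section 14.7 can also be read as covering the RCT results as a whole, including feasibility and safety summaries that all randomised participants can enter. The disagreement is between sections 14.7 and 15.1, and careful wording resolves it.
- **That the 6-month data are thrown away.** The synopsis names VO2max at 6 months as an outcome, section 15.1 uses 6-month fitness in a mediation analysis, and section 15.2 relates FitBit data to fitness at 6 and 12 months. The loss is confined to the 12-month models of five measures, for people without a 12-month value.
- **That the plan forecasts losing 30% of the RCT.** The 70% retention figure belongs to the cohort, and Enroll-HD will supply part of the 12-month data after someone is lost. Nor can the whole widening from 0.51 to 0.60 SD be recovered.
- **That the contrast will favour exercise.** Section 10.2 makes arm-dependent missingness possible, but the size and direction of bias are assumed.

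It also stands that the effect estimates are exploratory, without hypothesis tests, and that a bias of 0.06-0.15 SD is small beside a half-width of 0.60 SD. The SAP is not at hand and may say more. None of this removes the conflict, because the protocol itself fixes the missing-data method.

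**Conclusion.** The point holds as a moderate one. Sections 14.7 and 15.1 need reconciling, and complete case is a weak primary method for the five outcomes with a 6-month value, given a loss-to-follow-up rule that can act in one arm only. The precision gain is small and rests on the assumed 30% missingness, the assumed correlation and every leaver having a 6-month value. The stronger reason is reduced bias, which depends on assumed differential missingness. The first secondary objective, exploring effect estimates, is what is touched.

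**What to change.** 1. In section 15.1, say participants are analysed in the arm to which they were randomised.
2. For predicted VO2max, accelerometry, IPAQ, Lorig self-efficacy and the 6-minute walk, use a linear mixed model for repeated measures with arm by visit, baseline value, country and the minimisation factors. Include every randomised participant with at least one post-baseline value. Report the 6-month contrast (the named time point for VO2max) and the 12-month contrast. Keep complete case as a sensitivity analysis. Make Table 3 agree with Table 1 on the 6-month walk test.
3. For outcomes with one follow-up (Enroll-HD measures, Q-Motor, Q-Cog and HD-PRO-TRIAD at 12 months; C3T at 6 months), keep the adjusted regression and state that it includes participants with the outcome observed. Multiple imputation is optional here.
4. Amend section 14.7 to match, since even the mixed model leaves out anyone with no post-baseline value.

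The cost is wording and modest programming, with no new data. The mixed model relies on data being missing at random given the observed history.
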